## 2. INTRODUCTION

### 2.1. Study rationale

The aim of this study is to provide relative bioavailability data to support the transition from the vial presentation of bepirovirsen, which is currently under investigation in the Phase 3 trials, to a ready-to-use liquid in a PFS fitted with an SSD. The study in healthy participants is intended to demonstrate comparable bepirovirsen pharmacokinetics of SC injections of:

- Vial and PFS SSD presentations, when administered by an HCP; and
- HCP administration and self-administration of the PFS SSD.

Safety and tolerability will also be assessed.

### 2.2. Background

HBV infection, especially chronic infection, is a significant worldwide medical problem. Globally, in 2019, an estimated 296 million people were living with chronic HBV infection. Viral hepatitis led to 1.34 million deaths and of these deaths, 66% were the result of complications of chronic HBV infection [WHO, 2017; WHO, 2021].

The goal of therapy for chronic HBV infection is to improve quality of life and survival by preventing progression of the disease to cirrhosis, decompensated liver disease, end stage-liver disease, HCC, or death. This goal can be achieved if HBV replication is suppressed in a sustained manner, thereby decreasing the histological activity of chronic HBV infection and reducing the risk of cirrhosis and HCC [Liaw, 2004; Feld, 2009]. In both HBeAg positive- and -negative chronic HBV infection, the ultimate treatment endpoint is loss of detectable serum HBsAg [Lok, 2017; EASL, 2017]. However, despite treatment with approved therapies, including nucleoside or nucleotide (nucleos(t)ide) analogue and/or pegylated interferon, rates of HBsAg loss following 12 months of treatment generally range- from 0% to 3% in most studies [Lok, 2017; EASL, 2017].

Bepirovirsen, an antisense oligonucleotide, was designed to inhibit the synthesis of HBV viral proteins. The binding site for bepirovirsen is present within all HBV mRNA and pgRNA. Bepirovirsen directly targets HBV RNAs via RNase H mediated degradation, resulting in the reduction of viral proteins, including HBsAg. Bepirovirsen treatment permits examination of reduction in serum levels (including HBsAg) and HBV RNA/DNA [Yuen, 2007]. Bepirovirsen allows resumption of a host immune response against HBV and infected cells and can induce HBsAg seroclearance.

Bepirovirsen Solution for Injection, **CCI** mg/mL is a single-use sterile liquid drug product supplied in a clear glass vial. A ready-to-use PFS assembled into an SSD has been developed which will be more convenient and may allow the ultimate goal of patient self-administration.

**CONFIDENTIAL**219239  
Protocol

The formulation is unchanged between vial and safety syringe device. Consequently the likelihood of clinically significant differences in the systemic exposure, efficacy or safety profile is considered to be low. The relative bioavailability study will compare bepirovirsen exposures (AUC and Cmax) between vial and PFS SSD to ensure comparable PK exposures. The study will also compare bepirovirsen exposures between HCP administration and self-administration using the PFS SSD presentation.

A full description of the liquid drug product (vial and PFS SSD) is given in the Investigators' Brochure Supplement [GSK Document No.: [RPS-CLIN-035276](#)].

### **2.3. Benefit/risk assessment**

More detailed information about the known and expected benefits and risks, and reasonably expected AEs of bepirovirsen may be found in the IB [GSK Document No.: [RPS-CLIN-035276](#)].

CONFIDENTIAL

219239  
Protocol

### 2.3.1. Risk assessment

Relevant risks associated with bepirovirsen treatment in this study are summarized in [Table 4](#). A thorough description of all risks is included in the IB (Section 6). Additional monitoring for liver chemistry, DIVI, platelet count, renal function are discussed in Section [7.1](#). For a [CCI](#) dose administration of [CCI](#) mg, the risks are of low likelihood but cannot be ruled out.

**Table 4 Risk Assessment**

Potential Risk of Clinical Significance	Summary of Data/Rationale for Risk	Mitigation Strategy
Study Intervention(s) [Bepirovirsen]		
Non-clinical Risks:		
Drug Induced Vascular Inflammation (DIVI) and Complement Activation	Inflammatory and immune changes are recognized as a class effect of ASOs. Vasculitis and/or perivascular inflammation has been described in monkey studies with many, if not most ASOs. DIVI has not been observed in clinical studies with bepirovirsen to date.	Laboratory Evaluations: Inclusion of tests for biomarkers of inflammation/complement activation that would be expected to accompany vascular injury are to be taken at the time of a clinical event that is suggestive of vasculitis and/or immune activation and compared to referenced baseline measurements. A monitoring strategy is included (see Section 7.1.4 ).
Clinical Risks:		
Serious liver injury	The liver is a site of accumulation of ASOs. Liver findings in nonclinical studies of bepirovirsen were generally limited to mild hepatic enzyme elevations associated with hepatic vacuolation without concomitant histologic evidence of degeneration in mice, consistent with findings noted with other 2'-methoxyethyl (MOE) ASOs. Review of the	The risk of serious liver injury is very low after a single dose of bepirovirsen. Nevertheless, hepatic enzyme monitoring will be performed (see Section 7.1.1 ).

CONFIDENTIAL

219239  
Protocol

Potential Risk of Clinical Significance	Summary of Data/Rationale for Risk	Mitigation Strategy
	
available clinical data indicates liver enzymes are increased on treatment with ASOs (for treatment of diseases other than chronic HBV infection) in a low percentage of patients compared to placebo. A prior single dose study in healthy volunteers (213725) did result in an ALT increase > ULN in 1 participant treated with CC1 mg bepirovirsen. This was not associated with other changes in liver chemistry (e.g., bilirubin, INR) and did not have a clinical consequence. Review of AE data and laboratory data in Phase 2a and Phase 2b studies in participants with CHB in which bepirovirsen was given weekly for 4 weeks and 24 weeks respectively and where ALT increases > 3xULN were observed, showed no evidence of DILI.
 
CC1
	
Injection site reactions	
ISRs have been reported with ASOs and reported in clinical studies with bepirovirsen. ISRs were the most common study treatment-related AEs with the majority reported as Grade 1 severity (mild). The majority of ISRs are reported as injection site erythema, injection site pain and injection site pruritus. Few events have led to treatment discontinuation.
	
Evaluations: Participants are assessed for ISRs at all visits as per the SoA.

CONFIDENTIAL

219239  
Protocol

Potential Risk of Clinical Significance	Summary of Data/Rationale for Risk	Mitigation Strategy
Study Procedures		
Blood drawn	Risks with phlebotomy include bruising, bleeding, infection, and nerve damage.	Procedures to be performed by trained personnel (i.e., study nurse).
Handling and usage risks associated with PFS SSD	The IMP will be administered by or under the supervision of health care professionals. Anticipated device effects are nonserious, effects are unlikely, improbable, occasional, or remote and any effects are due to user errors.	Instructions for use on how to handle and use the devices will be provided.

**CONFIDENTIAL**219239  
Protocol**2.3.2. Benefit assessment**

As this Phase 1 study will be conducted in healthy adult participants, there will be no direct benefit to study participants included in this study.

Participants in this study will contribute to the development of an improved delivery of treatment for patients with CHB.

**2.3.3. Overall benefit-risk conclusion**

Whilst there is no benefit of treatment to the participant in this study, measures have been taken to minimize the participant's risk of participation.

Approved

CONFIDENTIAL

219239  
Protocol

### 3. OBJECTIVES, ENDPOINTS AND ESTIMANDS

Objective(s)	Endpoint(s)
Primary	

 
To estimate the relative bioavailability of vial and PFS SSD for a single dose of bepirovirsen delivered by SC injection by an HCP in healthy participants
 
	
 
Cmax and AUC(0-inf) of bepirovirsen in plasma.
 

Secondary	

 
To estimate the relative bioavailability of HCP administered vs self-administration following HCP training for a single dose of bepirovirsen delivered by SC injection in healthy participants
 
	
 
Cmax and AUC(0-inf) of bepirovirsen in plasma.
 

 
To estimate the relative bioavailability of HCP administered vs self-administration with no HCP training for a single dose of bepirovirsen delivered by SC injection in healthy participants
 
	
 
Cmax and AUC(0-inf) of bepirovirsen in plasma.
 

Safety	

 
To compare the safety and tolerability of CCI CCI mg by randomized group.
 
	
 
Occurrences of AEs and SAEs
 
Change from baseline at each time point in clinical laboratory tests and vital signs
 

Exploratory	
CCI	

#### Primary estimand

The primary interest is to estimate the relative bioavailability, measured by Cmax and AUC(0-inf), following a **CCI** of bepirovirsen via PFS SSD versus a vial in healthy adult participants.

The primary PK estimands are described by the following attributes:

- Population:
 

Healthy male and female participants aged 18 to 55 years.
- Treatment Condition:
 

**CCI** of bepirovirsen injection administered via PFS SSD versus **CCI** of bepirovirsen administered via a vial.

**CONFIDENTIAL**219239  
Protocol

- Variables:

AUC(0-inf) and Cmax.

- Summary measure:

Ratio of geometric means of PFS SSD versus vials for Cmax and AUC(0-inf).

- Intercurrent Events:

Use of prohibited medication. This intercurrent event is not expected to impact the PK of bepirovirsen so a treatment policy strategy will be used, and the individual PK concentrations after the occurrence of the intercurrent event will still be included in the PK analysis.

Participants who did not receive **CCI** the injections and had an incomplete or erroneous dosing. A principal stratum strategy policy will be used, where the strata of interest is the group of participants who are able to receive the complete dose.

A supplemental estimand will also be analyzed as per the primary estimand, except for the intercurrent event of incomplete dosing will use a treatment policy strategy.

## **Secondary estimand(s)**

The secondary interest is to estimate the relative bioavailability, measured by Cmax and AUC(0-inf):

1. Following a **CCI** of bepirovirsen via PFS SSD versus self-administration of a single dose of bepirovirsen with HCP training
2. Following a **CCI** of bepirovirsen via PFS SSD versus self-administration of a single dose of bepirovirsen with no HCP training.

The secondary PK estimands are described by the following attributes:

- Population:

Healthy male and female participants aged 18 to 55 years.

- Treatment condition:

**CCI** dose of bepirovirsen administered via PFS SSD versus self-administration of a single dose of bepirovirsen with HCP training.

**CCI** dose of bepirovirsen administered via PFS SSD versus self-administration of a single dose of bepirovirsen with no HCP training.

**CONFIDENTIAL**219239  
Protocol

- Variables:

AUC(0-inf) and Cmax.

- Summary measure:

Ratio of geometric means of PFS SSD versus self-administration with HCP training and with no HCP training for Cmax and AUC(0-inf).

- Intercurrent Events:

Use of prohibited medication. This intercurrent event is not expected to impact the PK of bepirovirsen so a treatment policy strategy will be used, and the individual PK concentrations after the occurrence of the intercurrent event will still be included in the PK analysis.

Participants who did not receive **CCI** the injections and had an incomplete or erroneous dosing. A principal stratum strategy policy will be used, where the strata of interest is the group of participants who are able to receive the complete dose.

Supplemental estimands will also be analysed as per the secondary estimand, except for the intercurrent event of incomplete dosing will use a treatment policy strategy.

## **4. STUDY DESIGN**

### **4.1. Overall design**

This is a Phase 1, open-label, randomized study to investigate SC bepirovirsen when delivered via SC injection from vial or PFS SSD in healthy adult participants. The study will assess relative bioavailability, safety and tolerability, as well as the usability of the PFS SSD for self-administration.

A total of approximately **CCI** participants will each complete a single study session, in a parallel design, and will each take up to **CC** weeks to complete the study.

Participants will be screened within 28 days before dosing. They will attend the clinical unit the day before dosing (Day -1) and will remain inpatient until 2 days after dosing

**CONFIDENTIAL**219239  
Protocol

(Day 3). They will receive bepirovirsen [REDACTED] mg as [REDACTED] mg SC injections on Day 1, randomized 3:3:2:2 to:

[REDACTED]

[REDACTED]

The randomization will be stratified by body weight [REDACTED] [REDACTED]. The site of injection will be randomized in a 1:1:1 ratio to the upper arm, abdomen, or thigh in Groups 1 and 2, and in a 1:1 ratio to abdomen or thigh in Groups 3 and 4.

Participants will return for outpatient visits on Days [REDACTED]

Blood samples will be taken to measure levels of bepirovirsen and ADAs against bepirovirsen, and safety and tolerability will be assessed from before dosing and until the final visit. The observing HCP and participants in Groups 3 and 4 will complete questionnaires, respectively, during and after dosing, to assess usability of the PFS SSD for self-administration. Blood samples will also be taken for biomarker analysis before dosing and up to 48 h after dosing.

The study design schematic is presented in Section 1.2.

#### **4.2. Scientific rationale for study design**

Conducting the study in healthy participants mitigates the recruitment and patient burden limitations with administering a single dose of bepirovirsen to CHB patients. A population of healthy participants is frequently used in the assessment of the relative bioavailability of both small and large molecules. In addition, healthy participants are a suitable population for biopharmaceutical PK comparability studies, and the data can be extrapolated to other populations. In addition, usability of the PFS SSD can be reliably assessed in healthy participants via questionnaires to support design of the human factors summative evaluation.

[REDACTED]

[REDACTED]

[REDACTED].

Bepirovirsen has a half-life of approximately [REDACTED] in healthy subjects. A [REDACTED]

[REDACTED]

[REDACTED]

[REDACTED]

[REDACTED]

**CONFIDENTIAL**219239  
Protocol

A [cci] dose of bepirovirsen will be administered as [cci] injections at 1 of 3 injection sites (upper arm, abdomen, or thigh) when administered by an HCP, or at 1 of 2 injections sites (abdomen or thigh) when self-administered. Upper arm is not a feasible administration site for self-administration. To prevent bias and maintain balance in treatment groups, the injection site will be randomized in addition to the randomization for device. To minimize the impact of potential confounding factors and variability, the randomization will also be stratified by body weight as this has been associated with bepirovirsen exposure.

Collection of PK blood samples up to Day [cci] will ensure that the bepirovirsen plasma concentration-time profile is well described with the extrapolated portion of AUC(0-inf) below [cci].

The study will be open-label. This is acceptable because the primary and secondary endpoints are PK parameters, which are not subjective measures. Any potential for selection bias will be reduced by central randomization.

#### **4.2.1. Participant input into design**

Participant input into the study design is not deemed necessary for this Phase 1 clinical pharmacology study.

#### **4.3. Justification for dose**

A [cci] of bepirovirsen [cci] mg will be administered as [cci] mg SC injections provided as vials or PFS SSD on Day 1. [cci]  
[REDACTED]  
[REDACTED].

#### **4.4. End-of-study definition**

A participant is considered to have completed the study if the participant has completed all periods of the study including the last visit shown in the SoA.

The end of the study is defined as the date of the last visit of the last participant in the study.

### **5. STUDY POPULATION**

Prospective approval of protocol deviations to recruitment and enrollment criteria, also known as protocol waivers or exemptions, is not permitted.

#### **5.1. Inclusion criteria**

Participants are eligible to be included in the study only if all of the following criteria apply:

**CONFIDENTIAL**

219239

Protocol

AGE
1. Participant must be 18 to 55 years of age inclusive, at the time of signing the informed consent.
TYPE OF PARTICIPANT AND DISEASE CHARACTERISTICS
2. Participants who are overtly healthy as determined by medical evaluation including medical history, physical examination, laboratory tests, ECGs and vital signs.
WEIGHT
3. Body weight $\geq$ 50 kg and body mass index (BMI) within the range 19 to 29.9 kg/m  (inclusive).
SEX

4. Male and/or female.
 
a. There are no contraceptive requirements for male participants.
 
b. A female participant is eligible to participate if she is not pregnant or breastfeeding, and 1 of the following conditions applies:
 
 
• Is a WONCBP as defined in the protocol (Section 10.4)
 
 
OR
 
 
• Is a WOCBP and using a contraceptive method (for a period of 28 days before dosing) that is highly effective (with a failure rate of <1% per year), preferably with low user dependency, as described in Appendix 4 of the protocol during the study intervention period and for at least 7 days after the last dose of study intervention and agrees not to donate eggs (ova, oocytes) for the purpose of reproduction during this period. The investigator should evaluate the potential for contraceptive method failure (e.g., noncompliance, recently initiated) in relationship to the first dose of study intervention.
 
 
A WOCBP must have a negative highly sensitive pregnancy test (urine or serum as required by local regulations) within 24 hours before the first dose of study intervention.
 
 
• If a urine test cannot be confirmed as negative (e.g., an ambiguous result), a serum pregnancy test is required. In such cases, the participant must be excluded from participation if the serum pregnancy result is positive.
 
 
The investigator is responsible for review of medical history, menstrual history, and recent sexual activity to decrease the risk for inclusion of a woman with an early undetected pregnancy.

INFORMED CONSENT
5. Capable of giving signed informed consent which includes compliance with the requirements and restrictions listed in the ICF and in this protocol.

**CONFIDENTIAL**219239  
Protocol**5.2. Exclusion criteria**

Participants are excluded from the study if any of the following criteria apply:

Medical Conditions
1. History or presence of cardiovascular, respiratory, hepatic, renal, gastrointestinal, endocrine, hematologic, or neurological disorders capable of significantly altering the absorption, metabolism, or elimination of drugs; constituting a risk when taking the study intervention or interfering with the interpretation of data.
2. Abnormal blood pressure as determined by the investigator.
3. Lymphoma, leukemia, or any malignancy within the past 5 years except for basal cell or squamous epithelial carcinomas of the skin that have been resected with no evidence of metastatic disease for 3 years.
4. Participants with signs or symptoms suggestive of COVID-19 (e.g., fever, cough) within 14 days of inpatient admission.
5. Participants with any other medical conditions which, in the judgement of the investigator and Medical Monitor, could jeopardize the integrity of the data derived from that participant or the safety of the participant.
6. Platelets $<140 \times 10^9 / \text{L}$ .
7. ALT $>1.5 \times \text{ULN}$
8. Total bilirubin $>1.5 \times \text{ULN}$ (isolated total bilirubin $>1.5 \times \text{ULN}$ is acceptable if total bilirubin is fractionated and direct bilirubin $<35\%$ ).
9. Current or chronic history of liver disease or known hepatic or biliary abnormalities (with the exception of Gilbert's syndrome or asymptomatic gallstones).
10. QTcF $>450$ msec.
Prior/Concomitant Therapy
11. Past, current or intended use of over-the-counter or prescription medication [including herbal medications] within 7 days or 5 half-lives (whichever is longer) before dosing [Specific medications listed in Section 6.9 of the protocol may be allowed].
12. Current or prior use of creatine-containing supplements and intended use up to 50 days post-dosing.
13. Prior use of immunosuppressive drugs within 3 months before dosing or interferon within 12 months before dosing.
14. Prior treatment with any oligonucleotide or small interfering RNA (siRNA) within 12 months before dosing.

**CONFIDENTIAL**219239  
Protocol

Prior/Concurrent Clinical Study Experience
15. Loss of blood or blood products in excess of 500 mL within any 3-month period during the study.
16. Exposure to more than 4 new chemical entities within 12 months prior to the first dosing day.
17. Current enrollment or past participation in another investigational study in which an investigational intervention (e.g., drug, vaccine, invasive device) was administered within 5-half-lives (if known) or twice the duration of biological effect (if known), whichever is longer, or within the last 90 days (if half-life and duration of biological effect are unknown), before the first dosing day in the current study.
18. Current enrollment or past participation in this clinical study.
Diagnostic Assessments
19. Presence of HBsAg at screening or within 3 months before dosing.
20. Positive hepatitis C antibody test result at screening or within 3 months before dosing. NOTE: Subjects with positive hepatitis C antibody due to prior resolved disease can be enrolled, only if a confirmatory negative hepatitis C RNA test is obtained.
21. Positive hepatitis C RNA test result at screening or within 3 months before dosing. NOTE: Test is optional and subjects with negative hepatitis C antibody test are not required to also undergo hepatitis C RNA testing.
22. Positive pre-study drug/alcohol screen, including THC.
23. Positive HIV antibody test.
24. Cotinine levels indicative of smoking or history or regular use of tobacco- or nicotine-containing products within 6 months prior to screening.
25. A positive test for active COVID-19 infection at or before admission for the inpatient stay. The testing should be done using a molecular polymerase chain reaction (PCR) or antigen test approved by the country regulatory authorities.
Other Exclusion Criteria
26. Regular alcohol consumption within 6 months prior to the study defined as an average weekly intake of >14 units for males or females. One unit is equivalent to 8 g of alcohol: a half-pint (~240 mL) of beer, 1 glass (125 mL) of wine or 1 (25 mL) measure of spirits.
27. Regular use of known drugs of abuse, including THC.
28. History of sensitivity to bepirovirsen or components thereof or a history of drug or other allergy that, in the opinion of the investigator or Medical Monitor contraindicates their participation.

**CONFIDENTIAL**219239  
Protocol

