### **5.3.4. Other restrictions**

Participants will be asked to refrain from donating blood for the duration of their study participation.

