## 8. **STUDY ASSESSMENTS AND PROCEDURES**

- Study procedures and their timing are summarized in the SoA (Section 1.3). Protocol waivers or exemptions are not allowed.
- Adherence to the study design requirements, including those specified in the SoA, is essential and required for study conduct.

**CONFIDENTIAL**219239  
Protocol

- All screening evaluations must be completed and reviewed to confirm that potential participants meet all eligibility criteria. Subjects who have signed informed consent but are not eligible to proceed should be recorded in the eCRF with a status of 'screen failure'.
- The maximum amount of blood collected from each participant over the duration of the study, including any extra assessments that may be required, will not exceed 500 mL.
- Repeat or unscheduled samples may be taken for safety reasons or for technical issues with the samples.

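### Exclusion criterion 15 counts only blood lost during the study, so in practice it screens out almost nobody, and no criterion counts blood lost before entry

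*Protocol*

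**What the plan says.** Section 5.2 of the protocol opens its list with "Participants are excluded from the study if any of the following criteria apply". Criterion 15, in the group on prior and concurrent study experience, reads "Loss of blood or blood products in excess of 500 mL within any 3-month period during the study".

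Three other passages bear on it:

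- **Timing of the eligibility decision.** Section 8 states: "All screening evaluations must be completed and reviewed to confirm that potential participants meet all eligibility criteria".
- **Blood taken by the study.** Section 8 also sets a limit of 500 mL, with unplanned tests counted, on this quantity: "The maximum amount of blood collected from each participant over the duration of the study".
- **Donation.** Section 5.3.4 states: "Participants will be asked to refrain from donating blood for the duration of their study participation". Inclusion criterion 5 makes compliance with protocol restrictions part of consent.

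The nearest rule on earlier trials is criterion 17. It sets the interval since an investigational intervention as "within 5-half-lives (if known) or twice the duration of biological effect (if known), whichever is longer", with 90 days as the fallback when neither quantity is known. Criterion 16 counts new chemical entities.

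**The concern.** An exclusion criterion has to separate volunteers at the time eligibility is decided. Criterion 15 describes loss that, at screening, lies almost wholly in the future and is already limited by Sections 8 and 5.3.4. The loss that a screen on prior experience would be expected to catch, such as a recent donation or sampling in another trial, falls outside its stated time frame.

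The protocol's definition of an eligible participant requires strict adherence to the criteria, and Section 5 allows no waivers. Sites therefore have to apply the wording as it stands.

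The main stake is participant safety. The protocol states a figure of 500 mL per 3 months but does not apply it to someone who arrives having already lost blood. A lesser stake is the baseline for haemoglobin, haematocrit and red cell count, which are study tests (protocol Table 11) and feed the change-from-baseline and worst-case summaries in SAP Section 4.5.2.2.

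**Working it through.** No sample size or error rate is involved. The check compares the passages and adds volumes.

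**1. Can study sampling trigger criterion 15?** The trigger is a loss above 500 mL in a 3-month window inside the study. The Section 8 cap is at most 500 mL over the whole study, extra assessments included. Any window inside the study holds no more than the whole, so study sampling cannot exceed 500 mL in it. This holds whatever the study's length.

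**2. What could trigger it?** Only loss outside study sampling after consent: a bleed, a donation made despite the request in Section 5.3.4, or sampling by another concurrent study that gives no investigational intervention.

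**3. Does another criterion count earlier blood loss?**

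- Criterion 16: no, it counts chemical entities.
- Criterion 17: no, it is a washout by half-life or duration of effect. For illustrative half-lives of 4, 12, 24 and 72 hours, five half-lives is 5 × t½ / 24 = 0.8, 2.5, 5 and 15 days. Where twice the duration of effect is also short, someone sampled in another trial days or weeks before can pass.
- Inclusion 2 and exclusion 5: judgement-based, with no blood volume or haemoglobin limit.
- Screening schedule (Table 1): no item on donation or blood loss.

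By contrast, criteria 13, 14, 16 and 24 each state a look-back period before dosing or screening.

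**4. Size.** Let P be the loss shortly before consent and V the volume this study draws. Both are assumptions: the documents give only the 500 mL cap, and the sampling schedule is redacted. Totals P + V in mL:

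| P | V = 100 | V = 200 | V = 300 | V = 500 (cap) |
|---|---|---|---|---|
| 250 | 350 | 450 | 550 | 750 |
| 450 | 550 | 650 | 750 | 950 |
| 500 | 600 | 700 | 800 | 1000 |

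For P = 450, the ratio to 500 mL runs from 550 / 500 = 1.1 to 950 / 500 = 1.9. The threshold is passed once V is above 500 − 450 = 50 mL. For P = 250 it is passed only when V is above 250 mL. In every cell criterion 15 as written looks at V alone, V is at most 500, and nobody is excluded.

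**5. Do these losses fall within 3 months?** Day 64 is the latest day named in the visible schedule (Table 2, laboratory footnote) and is assumed to be the last visit. Under the day numbering in SAP Section 6.2.2, Day 64 is 63 days after dosing. Consent and donation 7 days before dosing give 7 + 63 = 70 days. With the full 28-day screening period the span is 28 + 63 = 91 days, at the edge of 3 months (90 to 92 days).

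**The case against.** The strongest reply is that the criterion can be read generously. It stands under a heading about prior experience and speaks of any 3-month period, so a site might count every window that overlaps the study, including loss before entry. That reading would make the rule work, but the text does not state it, and sites could differ. It is a reason to clarify the wording.

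A reader might also infer that criterion 15 excludes nobody at all, or that recent donors are certain to be let in. The documents do not support either. Section 5.3.4 is a request about blood donation and does not mention blood products, while criterion 15 covers both. The Section 8 cap covers only what this study collects. Loss after consent from another source could therefore still meet the criterion. Forward-looking criteria are also not unanswerable in principle: criteria 11 and 12 refer to intended use.

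It would likewise be wrong to say that criterion 17 sets no interval when the half-life is known. It does set one. What it lacks is a fixed calendar minimum, and entry within days requires both a short half-life and a short duration of effect.

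Existing safeguards deserve credit. Screening includes haematology, and inclusion 2 and exclusion 5 let the investigator turn away someone whose health or data would be compromised. They may catch a marked loss, but they do not apply the 500 mL figure.

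**Conclusion.** The point stands as a defect in a stated rule. Criterion 15 does almost no work as an entry screen, and nothing else in the protocol counts blood volume lost before the study.

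The range of 1.1 to 1.9 times the 500 mL figure rests on an assumed 450 mL donation just before consent, assumed draws of 100 to 500 mL, and Day 64 as the last visit. The upper end is a ceiling, because the cap allows for extra assessments and is not the planned volume. That the figure serves participant safety is inferred; the protocol does not give its purpose.

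The effect on haematology baselines is possible, probably minor, and not quantified. Those summaries are descriptive, and randomization gives no reason to expect recent donors to favour one group. A reader might infer that the vial versus prefilled syringe comparison is affected. Nothing in the documents shows that, and it is not claimed.

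**What to change.** Reconcile criterion 15 with Sections 5.3.4 and 8, keeping the sponsor's own 500 mL and 3-month figures. Word it so that it can be answered at screening and states that earlier loss counts. For example: *blood donated, sampled or otherwise lost in the 3 months before dosing, together with the volume planned for this study, would exceed 500 mL in any 3-month period.*

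The sum should use the planned sampling volume, which the sponsor knows. If the 500 mL cap were used instead, any earlier loss at all would exclude the volunteer, since 500 + P exceeds 500 for every P above zero.

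Add one item to the screening schedule in Table 1 to record donations and trial sampling in the previous 3 months.

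The cost is one sentence in Section 5.2 and one screening question. The downside is that a few recent donors or trial participants wait or are screened out.
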